6.3 Non-Serious Adverse Events

A *non-serious adverse event* is any AE not classified as serious.

6.3.1 Non-serious Adverse Event Reporting

Non-serious AEs should also be followed to resolution or stabilization, or reported as SAEs if they become serious (see Section 6.2.1). Follow-up is also required for non-serious AEs that cause interruption or discontinuation of study drug and for those present at the end-of-study treatment, as appropriate. All identified non-serious AEs must be recorded and described on the appropriate AE page of the CRF.

Completion of supplemental CRFs may be requested for AEs and/or laboratory abnormalities that are reported during the course of the study.

6.4 Laboratory Test Result Abnormalities

The following laboratory test result abnormalities should be captured on the appropriate CRF page or SAE Report Form as appropriate:

- Any laboratory test result that is clinically significant or meets the definition of an SAE
- Any laboratory test result abnormality that required the patient to have study drug discontinued or interrupted
- Any laboratory test result abnormality that required the patient to receive specific corrective therapy.

It is expected that wherever possible, the clinical rather than laboratory term would be used by the reporting Investigator (e.g., anemia versus low hemoglobin value).

6.5 Pregnancy

If, following initiation of the investigational product, it is discovered that a study patient is pregnant or may have been pregnant at the time of investigational product exposure, including during at least 5 half-lives after product administration, the investigational product will be permanently discontinued in an appropriate manner.

The Investigator must immediately notify the Industry Collaborators of this event and complete and forward a Pregnancy Form to the Sponsor (or designee) within 24 hours and in accordance with SAE reporting procedures described in Section 6.2.1.

Follow-up information regarding the course of the pregnancy, including perinatal and neonatal outcome and, where applicable, offspring information, must be reported on the Pregnancy Surveillance Form.

Any pregnancy that occurs in a female partner of a male study participant should be reported to the Sponsor. Information on this pregnancy will be collected on the Pregnancy Surveillance Form.

6.6 Overdose

Any dose of study drug in excess of 50% of the dose level specified in the protocol is considered to be an overdose. Signs and symptoms of an overdose that meet any SAE criterion must be reported as an SAE in the appropriate time frame and documented as clinical sequelae to an overdose. There is no known antidote for a drug overdose to either cabiralizumab or nivolumab. In the event of an overdose, patients should be closely monitored and given appropriate supportive treatment.

6.7 Potential Drug Induced Liver Injury

Wherever possible, timely confirmation of initial liver-related laboratory abnormalities should occur prior to the reporting of a potential drug-induced liver injury (DILI) event. All occurrences of potential DILIs, meeting the defined criteria, must be reported as SAEs.

Potential drug induced liver injury is defined as:

1. ALT or AST elevation $>3x$ ULN
and
2. Total bilirubin $>2x$ ULN ($> 2x$ baseline in patients with Gilbert's syndrome) without initial findings of cholestasis (elevated serum alkaline phosphatase) ***or*** INR $> 1.5 \times$ ULN (in the absence of anticoagulation)
and
3. No other immediately apparent possible causes of aminotransferase elevation and

hyperbilirubinemia including, but not limited to viral hepatitis, pre-existing chronic or acute liver disease, or the administration of other drugs known to be hepatotoxic.

7. Statistical Considerations

7.1 Sample Size Determination

The primary endpoint of safety and MTD of APX005M in combination with cabiralizumab and nivolumab will be determined by a 3+3 dose escalation design as described above. In this first phase, patients will be enrolled regardless of disease (melanoma, NSCLC, and RCC). The maximum tolerated dose (MTD) will be estimated independently of cohort. Upon completion of this determination, we will proceed to three parallel two-stage designs, separately for each of the three disease cohorts using the MTD. Patients exposed to the MTD in the dose escalation phase will be carried over to the appropriate two-stage design.

Simon's two-stage design will be used in the phase 1b portion of the trial which will include 3 separate and parallel disease-specific cohorts (melanoma, NSCLC, and RCC). For each of the three tumor types, an immune therapy regimen which is modestly active in patients whose disease had progressed on PD-1/PD-L1 inhibitors would have a response rate (RR) of 10%. The null hypothesis that the true response rate is 10% will be tested against a one-sided alternative. A regimen worthy of further investigation in any of the three tumor types will have a RR of 25%. In the first stage, 13 patients of each cancer will be accrued. If there are 1 or fewer responses in these 13 patients, that cohort will be stopped. Otherwise, 21 additional patients of the same disease cohort will be accrued for a maximum total of 34 patients per disease cohort. Each of the three null hypotheses will be rejected if 6 or more responses are observed in 34 patients for each cohort. This design yields a type I error rate of 0.1 and a power of 80% when the true response rate is 25% in each of the three cohorts. There will not be a correction for multiplicity across the three separate cohorts.

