If none of the first 3 evaluable patients in a dose cohort experience a dose-limiting toxicity (DLT) in the first two cycles, then the next 3 patients will be treated at the next higher dose cohort. If 1 of 3 patients within a cohort experiences a DLT in the first two cycles, then 3 additional patients will be added to that cohort. If a second patient experiences a DLT at that dose level in the first two cycles, the next cohort will not be initiated, and the dose of one or more drugs will be de-escalated. Patients at each dose level will be evaluated for at least 4 weeks from the start of treatment before additional patients can be treated at a higher dose level. If DLTs are observed in 2 or more patients within a cohort, the maximum tolerated dose (MTD) will have been exceeded and no further patients will be treated at that dose level. At 8 weeks, imaging studies will be performed to assess for response. Of note, 2 sets of cohorts will be conducted simultaneously: Cohorts 2 and 3, and Cohorts 4 and 5, as depicted below.

Dose escalation will be based on the number of DLTs experienced during the DLT evaluation interval as determined by dose escalation meetings attended by the PIs and Industry Collaborators (see Section 3.1.2.1.1 for DLT criteria). The DLT evaluation interval begins on the first day of treatment and continues for 28 days.

Algorithm for Dose-Escalation Decisions

Number of Patients with DLT at a Given Dose Level	Dose Escalation Decision Rule
0/3	Escalation will occur into the next highest dose cohort
1/3	Enroll 3 additional patients at current dose level
≥2/3	Stop enrolment. Enroll 3 more patients at the lower dose level, if only 3 were previously entered, or at an intermediate dose level.
1/6	Open next cohort
≥2/6	Stop enrolment. Enter 3 more patients at the lower dose level or at an intermediate dose level.

Phase 1b Study

Once a specific dose regimen is determined to be safe as determined by the Sponsors and Industry Collaborators, the phase 1b portion will follow and will enroll additional patients in three disease-specific cohorts, all of whom who have progressed on prior PD-1/PD-L1 therapy: advanced melanoma, NSCLC,

and RCC who have progressed on prior PD-1/PD-L1 therapy. Patients will be treated at the estimated APX005M RP2D in combination with nivolumab 240 mg IV and cabirizumab 4 mg/kg on day 1 of each 14-day cycle.

Number of Patients

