3.1 Study Design and Duration

This study is a Phase 1/1b, open-label, single institution, dose escalation and dose expansion study to evaluate the efficacy, safety, and tolerability of APX005M in combination with nivolumab and cabiralizumab in patients with advanced melanoma, NSCLC, and RCC.

Nivolumab is a fully human monoclonal antibody directed against PD-1. Cabiralizumab is a humanized monoclonal antibody directed against CSF1R. APX005M is a humanized IgG1 agonistic monoclonal antibody that binds CD40.

Patients will be sequentially enrolled in the phase 1 dose escalation portion in 6 cohorts using a standard 3 + 3 design to determine safety, characterize the adverse events, and establish the MTD of APX005M in combination with cabiralizumab and nivolumab. A minimum of 48 hours observation will be required after each patient is enrolled in cohorts 1-6, before a subsequent patient can be enrolled. Approximately 3 patients will be enrolled into each cohort. Cohorts 1, 3, and 5 will include cabiralizumab at the fixed RP2D of 4 mg/kg and dose escalation of APX005M. Cohorts 2, 4, and 6 will include nivolumab at 240 mg, cabiralizumab at 4 mg/kg, and dose escalation of APX005M.

All study drugs will be given on Day 1 of each 14-day treatment cycle. Pre-medications will be given before nivolumab. Nivolumab will be administered as an IV infusion over 30 minutes first followed by a 30-minute break and then cabiralizumab will be administered as an IV infusion over 30 minutes. After another 30-minute break, APX005M will be administered as an IV infusion over 60 minutes. Patients must remain near the vicinity of a hospital with rapid access to an intensive care unit setting during the initial 48 hour period after treatment for the first two treatment cycles.

Dose escalation will be based on the number of DLTs experienced during the DLT evaluation interval as determined by the PI and Industry Collaborators (see Section 3.1.2.1.1 for DLT criteria). The DLT evaluation interval begins on the first day of treatment and continues for 28 days.

The phase 1b portion will enroll patients in three cohorts (advanced melanoma, NSCLC, and RCC) to study the RP2D of APX005M in combination with nivolumab and cabiralizumab.

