The MTD is defined as the highest dose associated with DLTs in less than or equal to 33% of patients receiving APX005M in combination with cabiralizumab or with cabiralizumab and nivolumab, administered during the DLT period. This will normally be the dose recommended for further study; however, based on review of safety, PK, and PD (if available) data, the RP2D could be lower than the MTD. If the MTD is not reached, and the highest evaluated APX005M dose in combination with cabiralizumab and nivolumab is well tolerated, the data will be reviewed to assess whether further dose escalations of APX005M are warranted.

In order to calculate the MTD and RP2D, every patient included in this calculation must have received at least 2 doses of study drugs and have been monitored for at least 2 full cycles (28 days). If a patient does not receive 2 doses of study drugs and does not complete safety assessments (e.g., safety lab and/or AE reporting) in the first 28 days for reasons other than drug-

related AEs (e.g., disease progression or withdrawal of consent), then an additional patient will be enrolled into the cohort so that the cohort has at least 3 patients evaluable for 28 days. All such discussions and decisions will be documented as part of the dose escalation decision-making process.

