3.1.2.3 Phase 1b Expansion Cohorts

To further characterize safety and efficacy of APX005M in combination with nivolumab and cabirizumab, Phase 1b will enroll patients of 3 advanced cancer types: melanoma, NSCLC, and RCC. Enrollment in Phase 1b will begin when an RP2D for APX005M has been identified based on overall safety, tolerability, PK, and PD (if available) data.

During enrollment of any expansion cohort, if the observed number of responses makes it unlikely to achieve a target response rate for that indication, then further recruitment to that cohort may be suspended or terminated.

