4.4 Study Drug Dosing and Dose Modification

4.4.1 Dosing

Dosing calculations should be based on the body weight assessed at Cycle 1 Day 1 prior to the first dose of study drug administration. It is not necessary to recalculate subsequent doses if the patient's weight is within 10% of the weight used to calculate the previous dose. All doses should be rounded to the nearest milligram.

Patients should be carefully monitored for infusion reactions during study drug administration. If an acute infusion reaction is noted, patients should be managed according to the guidelines in Section 4.8 and Section 4.9. Patients must remain near the vicinity of a hospital with rapid access to an intensive care unit setting during the initial 48 hour period after treatment for the first two treatment cycles.

All vials are for single use only. Further instructions on study drug preparation and administration are provided in the Pharmacy Manual.

Please refer to the study schema for dosing as follows:

- Phase 1 Dose Escalation (Dosing on Day 1 of each 14-day cycle):
 - Cohort 1: Cabiralizumab 4 mg/kg + APX005M 0.03 mg/kg
 - Cohort 2: Nivolumab 240 mg + Cabiralizumab 4 mg/kg + APX005M 0.03 mg/kg
 - Cohort 3: Cabiralizumab 4 mg/kg + APX005M 0.1 mg/kg

- Cohort 4: Nivolumab 240 mg + Cabiralizumab 4 mg/kg + APX005M 0.1 mg/kg
- Cohort 5: Cabiralizumab 4 mg/kg + APX005M 0.3 mg/kg
- Cohort 6: Nivolumab 240 mg + Cabiralizumab 4 mg/kg + APX005M 0.3 mg/kg
- Phase 1b (Dosing on Day 1 of each 14-day cycle):
 - ALL patients: Nivolumab 240 mg + Cabiralizumab 4 mg/kg + APX005M at the RP2D

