4.4.1.3 APX005M Dosing

All patients in all cohorts of the trial will receive APX005M as follows:

- Phase 1:
 - Cohorts 1 and 2: APX005M 0.03 mg/kg
 - Cohorts 3 and 4: APX005M 0.1 mg/kg
 - Cohorts 5 and 6: APX005M 0.3 mg/kg
- Phase 1b:
 - At the determined RP2D

APX005M is administered on Day 1 of each 14-day treatment cycle approximately 30 minutes following cabiralizumab using a 60 minute IV infusion. A window between -5 minutes and +10 minutes is permitted (i.e., infusion time is 55 minutes to 70 minutes).

Premedication should have already been administered 30 minutes prior to first dose of study drug, as described in Section 4.4.1.1. When the time between premedication and scheduled APX005M administration exceeds 4 hours, patients may receive an additional course of premedication prior to APX005M administration.

The APX005M infusion can be interrupted in the case of a grade 1-2 infusion reaction (see Section 4.8 and Section 4.9). Once symptoms resolve, infusion should be restarted at 50% of the initial infusion rate (e.g., from 50 mL/hr to 25 mL/hr). For a grade 3 infusion reaction, APX005M should be held and the investigator should dose reduce with the next cycle. Grade 4 infusion

reactions require discontinuation of APX005M.

The Pharmacy Manual contains specific instructions for the preparation of the APX005M infusion and administration of infusion solution.

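### Section 7.1 selects phase 1 patients for the phase 1b response test by exposure to the MTD, although phase 1b is given at the RP2D, which may be lower; the effect is minor and conditional

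*Combined protocol and SAP*

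**What the plan says.** Section 7.1 (Sample Size Determination) says that, once dose escalation is complete, three two-stage designs will run "separately for each of the three disease cohorts using the MTD". Its next sentence is the carry-over rule: "Patients exposed to the MTD in the dose escalation phase will be carried over to the appropriate two-stage design". No other section mentions carry-over.

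Five other places describe the phase 1b dose, and all of them use the RP2D:

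- Synopsis, Phase 1b Study: "Patients will be treated at the estimated APX005M RP2D in combination with" the two fixed-dose drugs.
- Section 3.1: the expansion cohorts are enrolled "to study the RP2D of APX005M in combination with nivolumab and cabiralizumab".
- Section 3.1.2.3: "Enrollment in Phase 1b will begin when an RP2D for APX005M has been identified".
- Section 4.4.1: "ALL patients: Nivolumab 240 mg + Cabiralizumab 4 mg/kg + APX005M at the RP2D".
- Section 4.4.1.3, on APX005M in phase 1b: "At the determined RP2D".

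Section 3.1.2.1 links the two terms. Of the MTD it says "This will normally be the dose recommended for further study", then adds that review of safety, PK and PD data could lead to an RP2D below it. The same section lets escalation end at the highest planned dose and treats an MTD that is not reached as a separate outcome. For that outcome it asks only for a data review on whether to escalate further.

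**The concern.** A carry-over rule should bring in patients who received what the phase 1b patients receive. This one selects by a quantity that the protocol itself says may differ from the phase 1b dose. Two foreseen outcomes expose the gap.

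1. **RP2D below the MTD.** Read literally, phase 1 patients treated at a higher APX005M dose enter the primary response test, and those already treated at the phase 1b dose do not.
2. **No MTD reached.** The rule has nothing to refer to, so it carries over nobody or is undefined.

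The cut-offs are tight: 1 versus 2 responses in 13 decides whether a disease cohort continues, and 6 in 34 decides success. One or two patients who do not belong can therefore matter. The stated error rates assume one common response rate among all counted patients.

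**Working it through.** **Inputs (Section 7.1).** Null response rate 10%, alternative 25%, one-sided. Stage 1 has 13 patients per disease, with a stop at 1 or fewer responses. Stage 2 adds 21, for a total of 34. Reject at 6 or more responses. Stated type I error 0.1, power 80%.

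**Step 1: the plan's own figures.** With X1 ~ Binomial(13, p) and X2 ~ Binomial(21, p),

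P(reject) = sum over x = 2 to 13 of P(X1 = x) × P(X2 ≥ 6 − x).

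- p = 0.10: 0.2448 × 0.1520 + 0.0997 × 0.3516 + 0.0277 × 0.6353 + 0.0055 × 0.8906 + 0.0009 (x ≥ 6) = **0.0957**.
- p = 0.25: 0.1664 + 0.2329 + 0.2057 + 0.1255 + 0.0802 (x = 2, 3, 4, 5, ≥ 6) = **0.8108**.

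Both agree with the stated 0.1 and 80%. The design is sound; the question is who enters the 13 and the 34.

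**Step 2: how many patients could be miscounted.** The documents do not say. Table 3 in Section 3.1.2.1 puts 3 to 6 patients in a cohort. Spread over three diseases, one triplet cohort supplies on average 3/3 = 1 to 6/3 = 2 per disease. I take one or two as an assumption; an uneven split would put more in one disease and fewer in the others.

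**Step 3: type I error with miscounted patients.** The true rate at the phase 1b dose is 10%. The miscounted patients respond at an assumed rate q of 15% to 25%; the documents give no figure. Section 7.1 does not say which stage carried-over patients join, so both placements are shown.

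*One patient among the first 13.* P(reject) = (1 − q) × R0 + q × R1, where R0 and R1 are the rejection probabilities if that patient does not or does respond. R0 = 0.0824. At q = 0.10 the mixture must return 0.0957, so R1 = (0.09571 − 0.9 × 0.08239)/0.1 = 0.2156.

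- q = 0.15: 0.85 × 0.0824 + 0.15 × 0.2156 = 0.1024
- q = 0.25: 0.75 × 0.0824 + 0.25 × 0.2156 = 0.1157

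*Two patients among the first 13.* The rejection probabilities given 0, 1 or 2 responses from the pair (the other 11 at 10%) are 0.0699, 0.1951 and 0.3997.

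- q = 0.15: 0.7225 × 0.0699 + 0.255 × 0.1951 + 0.0225 × 0.3997 = 0.1092
- q = 0.25: 0.5625 × 0.0699 + 0.375 × 0.1951 + 0.0625 × 0.3997 = 0.1375 (13.7% before rounding the terms)

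*Placed in stage 2 instead.* Stage 1 is Binomial(13, 0.10); stage 2 is Binomial(21 − k, 0.10) + Binomial(k, q) for k miscounted patients.

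| Miscounted patients | Within first 13 | Within stage 2 |
|---|---|---|
| none | 9.57% | 9.57% |
| one, q = 15-25% | 10.2-11.6% | 10.0-10.8% |
| two, q = 15-25% | 10.9-13.7% | 10.4-12.1% |

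If the miscounted patients also respond at 10%, the figure stays at 9.57%. If they respond less often, it falls: at q = 0 among the first 13, to 8.2% for one and 7.0% for two.

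**Step 4: the other branches.** If RP2D and MTD are equal, the counted patients have the phase 1b dose and Step 1 applies. If nobody is carried over, all 34 are newly enrolled and Step 1 again applies exactly. Leaving out patients treated at a planned triplet dose that becomes the RP2D forgoes 3 to 6 of the 3 × 13 = 39 stage 1 places (8-15%) but distorts nothing.

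**The case against.** The strongest reply is that this is a slip of terms. Section 7.1 is consistent within itself: it runs the designs at the MTD and carries over patients from the MTD, so the intent is evidently to pool patients on one dose. Section 3.1.2.1 expects the two doses to coincide. A tolerated top dose could also meet the words of the MTD definition (DLTs in no more than 33% of patients), which would close the no-MTD gap. The intent is indeed plain, and the usual case is harmless. But the rule operates as written, Section 3.1.2.1 foresees a lower RP2D, and it treats an unreached MTD as a separate outcome. The wording should therefore be settled.

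A reader might infer three stronger things that the documents do not support:

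- **That the plan loses power.** A miscounted patient in this branch received a higher APX005M dose than the phase 1b patients. A loss of power needs such patients to respond worse. Nothing in the documents suggests that, and Sections 1.3.6.3.1 and 1.3.6.3.3 describe immune activation that rises with dose.
- **That patients could be picked on known responses.** The carry-over is worded as mandatory, and Sections 3.1.2.1 and 3.1.2.3 base the RP2D on safety, tolerability, PK and PD, not on tumour response.
- **That the unreached-MTD case damages the test.** Carrying over nobody leaves the error rates as stated.

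**Conclusion.** The point holds as a defect of wording with a minor, conditional effect. In one branch that the protocol foresees, the only stated rule yields the wrong set of patients for the primary response test. In another it yields none or is undefined, at a cost in usable patients only.

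The type I error range of 10.0% to 13.7% rests on one or two miscounted patients per disease and on their responding at 15-25% when the true rate at the phase 1b dose is 10%. Both are assumptions. It would be wrong to conclude that the Simon design is miscalibrated: its arithmetic reproduces, and it applies unchanged whenever every counted patient received the phase 1b regimen and dose. The sentence is still worth correcting, because the remedy is cheap and the cut-offs turn on single responses. Confidence is medium, because whether the RP2D will differ from the MTD cannot be known from the documents.

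**What to change.** Replace the carry-over sentence in Section 7.1 with one that depends on the regimen received, for example:

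> Phase 1 patients assigned at Cycle 1 Day 1 to the same nivolumab, cabiralizumab and APX005M regimen and dose as phase 1b patients, and who meet the phase 1b eligibility criteria, will be counted among the 13 (and 34) patients of their disease cohort, regardless of observed response and whether or not an MTD is declared.

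The assignment at Cycle 1 Day 1 is named because Section 4.10 permits later APX005M reductions, which would leave a bare reference to the same dose open to argument. The sentence also covers phase 1 patients who received no nivolumab and the uveal melanoma exclusion that applies only to phase 1b. Counting within the 13 and 34 is a design choice on which Section 7.1 is silent, and the sponsor should confirm it.

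Separately, reconcile the statement in Section 7.1 that the designs use the MTD with the RP2D wording in the Synopsis and Sections 3.1, 3.1.2.3, 4.4.1 and 4.4.1.3. This review takes no position on which dose governs.

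The cost is a wording amendment with HIC approval under Section 9.1.1 and a consistency check of those sections. A few phase 1 patients may no longer count and would have to be replaced by new enrolment, while those treated at the phase 1b regimen and dose would count.
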